# **EpiNet-First Trial 3**

EpiNet-*First* Trial-3 will compare levetiracetam and lamotrigine in patients with generalised onset seizures who are not prepared to take valproate. The entry criteria will be the same as for EpiNet-*First* Trial-2 except that patients are not prepared to take valproate, or their doctors are not prepared to randomise them to this drug.

#### Rationale

Prior to the publication of SANAD-I, lamotrigine was considered a first line alternative for patients with generalised onset seizures, but data from SANAD-I show that it is significantly less effective than valproate in this patient group(9). However, lamotrigine is considerably less teratogenic than valproate and is generally regarded as a drug of choice for women with epilepsy who wish to become pregnant(8).

SANAD-I demonstrated that sodium valproate is more effective than lamotrigine in patients with generalized seizures, but there remains uncertainty regarding the relative merits of lamotrigine and levetiracetam in patients for whom sodium valproate is not suitable. Patients with generalized-onset seizures who are eligible for an EpiNet-First study will therefore be stratified. If both levetiracetam and sodium valproate would be acceptable AEDs, then patients will be enrolled in EpiNet-First Trial 2 and be randomised to one of these drugs. However, if sodium valproate is deemed unacceptable, patients will be entered into EpiNet-First Trial-3 and randomised to either lamotrigine or levetiracetam.

Entry criteria for EpiNet-*First* Trial-3 will be exactly the same as for EpiNet-*First* Trial 2, apart from the appropriateness of valproate

# **EpiNet-First Trial 4**

The EpiNet-First Trial 4 will compare levetiracetam, lamotrigine and valproate in patients with seizures that cannot be classified. If patients are not willing to take sodium valproate, they will be randomised to either levetiracetam or lamotrigine (EpiNet-First Trial 5.)

#### Rationale

The SANAD-1 Arm B combined patients who had generalised seizures with those whose seizures could not be classified. We are concerned that combining these groups mixes patients whose seizures may respond to different drugs. In particular, we are concerned that some patients whose seizures are unclassified are likely to have focal seizures, and these patients may respond to different AEDs from patients with generalised seizures. We do not think that SANAD-1 B has informed physicians what the optimal treatment is for patients where the doctor is genuinely unsure of the nature of the seizure type. We are not convinced that SANAD-1 B has shown that valproate is superior to lamotrigine in this patient group(9). We are therefore comparing levetiracetam, lamotrigine and valproate in this trial.

We think it is important to include this arm of the trial because we want to allow investigators the option of including as many patients with newly diagnosed epilepsy who are being started on an AED as possible. We do not want patients with unclassified seizure types being squeezed into the group with generalised seizures, or the group with definite focal seizures.

# EpiNet-First Trial 5

#### Rationale

As discussed above, valproate may not be deemed appropriate for some patients - particularly women of child-bearing age. Patients with unclassified seizures who are eligible for the EpiNet-*First* study will therefore be stratified. The investigator will be asked whether all of levetiracetam, lamotrigine and sodium valproate would be acceptable AEDs, and if so, the patient will be randomised to one of these three AEDs. If sodium valproate is deemed unacceptable, patients will be entered into EpiNet-*First* Trial 5 and randomised to either lamotrigine or levetiracetam.

Entry criteria for EpiNet-First Trial 5 will be exactly the same as for EpiNet-First Trial 4, apart from the appropriateness of valproate

# 2.3 Objectives

**EpiNet-First-Trial 1** - To determine whether levetiracetam is more effective than either lamotrigine or carbamazepine when used as monotherapy in patients with untreated focal-onset seizures.

**EpiNet-First Trial 2** - To determine whether levetiracetam is more effective than valproate in patients with untreated generalised-onset seizures. (Patients with absence seizures alone are not included.)

**EpiNet-First-Trial 3** — To determine whether levetiracetam is more effective than lamotrigine in patients with untreated generalised-onset seizures for whom valproate is not suitable. (Patients with absence seizures alone are not included.)

**EpiNet-First-Trial 4** - To determine whether levetiracetam is more effective than lamotrigine or valproate in patients with untreated seizures of uncertain nature.

**EpiNet-First-Trial 5** - To determine whether levetiracetam is more effective than lamotrigine in patients with untreated seizures of uncertain nature, for whom valproate is not suitable.

A full list of outcome measures is presented in section 4.

#### 2.4 Potential Risks and Benefits

The recruiting clinician will discuss the potential risks and benefits with patients prior to trial entry and they will be outlined in the patient information sheet.

# 2.4.1 Known Potential Risks

None of the AEDs being studied in the EpiNet-First group of trials are experimental drugs. All of them have been registered and are in widespread use in many countries over a number of years. The risk profiles are well known. People who have the HLA-B\*1502 haplotype have a significant risk if they are given carbamazepine; otherwise, there is a small risk of an idiosyncratic drug reaction for any of these AEDs. The main risk of EpiNet-First is that patients may be allocated to a treatment that on final analysis is found to be less effective than another treatment, or have a higher adverse event rate. However, there is currently clinical equipoise among the treatments being tested. Participants can be switched from their allocated treatment if a decision is made by the prescribing physician and patient that seizure control is inadequate or adverse events are unacceptable.

# 2.4.2 Known Potential Benefits

Patients recruited into the EpiNet-First trials will receive standard care during the conduct of the trials. The main potential benefit is that patients might receive treatment with a drug which is either more effective and/or better tolerated than the alternative treatment.

Their participation will help determine which of the AEDs being studied is the more EpiNet-First Study Protocol Version 1.0 Dated 15/04/14

trial than may ha	ve occurred in other	circumstances.		

# 3. SELECTION OF CENTRES / CLINICIANS

The EpiNet-First trials will take place in out-patient epilepsy clinics, general neurology clinics and paediatric (epilepsy and general) clinics in any centre in the world where there are approved EpiNet investigators who have received the appropriate approvals from their ethics committees and local research body. The study will be coordinated through the EpiNet-First coordinating centre which will be based in Auckland, New Zealand.

A formal validation test of the EpiNet study group is currently underway. Only investigators who provide acceptable results in the validation study will be accredited to participate in the EpiNet-*First* trials. Accreditation records will be kept at the coordinating centre in Auckland, New Zealand and kept in the study file.

Study centres will be initiated once ethics approval and any local R&D/locality approvals have been obtained, and study-specific conditions (e.g. training and accreditation requirements) have been met, and all necessary documents have been returned to the coordinating centre (which can be done electronically as a PDF file).

This protocol covers all five of the EpiNet-First trials, and these trials will be run simultaneously. However, particular centres and investigators do not need to participate in all 5 trials. For various reasons (such as a high prevalence of HLA B\*1502 haplotype), some centres may decide not to participate in a particular trial. Individual investigators may therefore participate in anywhere between one and five of the EpiNet-First trials.

# 3.1 Centre / Clinician Inclusion Criteria

- a. Experienced in treating pilepsy.
- b. Ethical and Local organisational approvals.
- c. Each of the AEDs being studied in a particular trial is registered in the country.
- d. Accreditation of investigator by successful participation in the EpiNet Validation study.
- e. Receipt of evidence of completion of (b) and (d) by the coordinating centre.

#### 3.2 Centre / Clinician Exclusion Criteria

a. Not meeting all the inclusion criteria listed above

#### 4. TRIAL DESIGN

# 4.1 Primary Endpoint

The primary endpoint for each of the 5 EpiNet-*First* trials is time to 12 month remission from seizures; the time (T0) will start from the date of randomisation, even if the patient commences the AED on another day. (The time will be taken from the date of randomisation, rather than the date of the last seizure which preceded randomisation.)

# 4.2 Secondary Endpoint(s)

- a. Time to treatment failure, due to either inadequate seizure control, or due to unacceptable adverse events. Treatment failure due to inadequate seizure control will have occurred when the clinician and/or patient decide that treatment withdrawal, or the addition of a second antiepileptic drug is required due to the occurrence of a seizure on the maximum recommended dose of randomised drug, or the maximum tolerated dose of the drug; treatment failure due to unacceptable adverse events will have occurred when the patient experiences adverse events attributed to the drug necessitating its withdrawal.
- b. Time to treatment failure due to inadequate seizure control.
- c. Time to treatment failure due to unacceptable adverse events.
- d. Time to first seizure;
- e. Time to 24 month remission;
- f. Serious Adverse events attributed to the trial medication or other anti-epileptic medication;
- g. Proportion of patients who achieve a 12 month remission by 18 months who have not changed to a different AED;
- h. Quality of life (QOL) (assessed using QOLIE31)(37)

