# 5.3.1 Cessation/Change of AED Treatment

If withdrawal of the randomly allocated treatment occurs (either due adverse events or insufficient efficacy), or additional AEDs are added to the randomly allocated treatment patients should still be followed up to allow a thorough assessment of the treatment policies, as patients may still achieve the primary outcome (12 month remission) following withdrawal of randomised treatment.

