#### 7.7 Dose Modifications

The aim of treatment will be to control seizures with a minimum effective dose of drug. This will necessitate dosage modification if further seizures or adverse events occur, as is usual clinical practice. The decision to discontinue allocated trial treatment is at the discretion of the treating physician and patient. Treatment may be discontinued at any point during the trial period for reasons such as inadequate seizure control, unacceptable adverse events, or any change in the participant's condition that the physician believes warrants a change in medication. Any changes in medication must be documented in the EpiNet record along with the reason for those changes. If a participant's treatment stops prematurely, the reason for discontinuation should be recorded in the EpiNet record, and the patient should still be encouraged to attend follow up visits for the remainder of the study.

At the end of trial participation the participants may continue their treatment as per local policy.

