# 9.5 Analysis Plan

All participants who are invited to participate in EpiNet-First trials will be accounted for and a CONSORT statement prepared. A table summarizing the number of participants who have assessed for eligibility, registered in each trial and been randomized for participation, will be provided. Participant disposition will be presented in one or more figures.

Demographic data collected on all randomised participants will be summarized. Summaries of continuous variables which are normally distributed will be presented as means and standard deviations or medians and inter-quartiles for skewed data, while categorical variables will be presented as frequencies and percentages.

Treatment evaluations will be undertaken for each trial separately. The primary outcome will be summarised by Kaplan-Meier curves and compared between the treatment groups using the log rank test. Cox proportional hazards regression models will be used in two different ways: (i) including the treatment effect only, using treatment indicator variables (ii) including the treatment effect together with stratification factors and important baseline covariates. The impact of country effect on the treatment comparison will be controlled by considering a random effect in the regression analysis. A similar analysis strategy will be employed for the other secondary time to event outcomes. For time to treatment failure, further analysis will be undertaken to assess the two main reasons for treatment failure-inadequate seizure control and unacceptable adverse effects. To allow for possible dependence between the different withdrawal risks, cumulative incidence analyses will be presented(39).

The proportion of patients who achieve a 12 month remission by 18 months who have not changed to a different AED will be compared between treatment groups using simple chi-squared test with estimation of relative risks and 95% confidence EpiNet-First Study Protocol Version 1.0 Dated 15/04/14

intervals. Logistic regression analysis will also be conducted adjusting for stratification factors and important baseline covariates.

QOL data will be analysed longitudinally to explore between treatments differences in scale scores overtime, taking account of stratification factors, baseline QOL and other important covariates. Line listings will be prepared for all serious adverse events.

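### Treatment failure for seizures counts only stops at the maximum recommended or tolerated dose, but stopping for seizures carries no dose condition, so some efficacy failures are uncounted

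*Protocol*

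**What the plan says.** Section 4.2(a) defines treatment failure with two limbs. The seizure-control limb, which also defines endpoint (b), is met when clinician or patient decides on withdrawal or on a second AED "due to the occurrence of a seizure on the maximum recommended dose of randomised drug, or the maximum tolerated dose of the drug". The adverse-event limb is met "when the patient experiences adverse events attributed to the drug necessitating its withdrawal".

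The sections on stopping and switching set no dose condition:

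- Section 2.4.1: "Participants can be switched from their allocated treatment if a decision is made by the prescribing physician and patient that seizure control is inadequate".
- Section 5.3.1, on follow-up after treatment changes: "If withdrawal of the randomly allocated treatment occurs (either due adverse events or insufficient efficacy".
- Section 7.7: "The decision to discontinue allocated trial treatment is at the discretion of the treating physician and patient", and "Treatment may be discontinued at any point during the trial period for reasons such as inadequate seizure control, unacceptable adverse events". The same section requires every medication change to be documented with its reason.

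Section 9.5 says that further analysis of time to treatment failure will "assess the two main reasons for treatment failure-inadequate seizure control and unacceptable adverse effects", using cumulative incidence to allow for dependence between withdrawal risks. Section 7.4 states that the trials are open-label. Section 7.3 lets clinicians choose titration and initial maintenance.

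**The concern.** The protocol permits an event that its failure definition does not classify: the allocated drug is given up because of seizures before the maximum recommended or tolerated dose is reached. In practice that is an efficacy failure of the treatment policy, and section 7.5 says that the trials aim to measure treatment policies as they work in ordinary care.

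Two things are at stake. The first is undercounting. Such patients drop out of time to treatment failure, or are censored at the switch. That censoring is informative, because they leave precisely because the drug is not controlling their seizures.

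The second is comparability of the arms. How far a clinician titrates before giving up is an unblinded decision. Section 2.2 reports that carbamazepine (focal seizures) and valproate (generalised seizures) are widely seen as drugs of first choice, and both are comparators to levetiracetam. If clinicians persist longer with one drug than another, the share of efficacy failures that qualify will differ between arms even when the drugs perform equally.

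**Working it through.** **Text comparison.** Take a patient on the allocated drug, below the maximum recommended dose and not limited by side effects, who has further seizures and is switched to another AED.

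| Provision | Result for this patient |
|---|---|
| 2.4.1, 5.3.1, 7.7 | Switch permitted; reason recorded as inadequate control |
| 4.2(a)/(b), seizure limb | Not met: seizure was not on the maximum recommended or tolerated dose |
| 4.2(a)/(c), adverse-event limb | Not met: no adverse event made withdrawal necessary |
| 4.2(g), 12 month remission by 18 months without changing AED | Disqualified by the change of AED, at any dose |
| 4.1, time to 12 month remission | Unaffected: follow-up continues after treatment changes (5.3, 5.3.1) |

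One switch is thus a lost success under (g) and a non-event under (a) and (b).

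**Size.** The protocol gives no figure to reproduce. Section 9.2 sizes the trials on 12 month remission, and nothing is stated about expected treatment failure. All shares below are assumptions.

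*Recorded risk.* Recorded failure = (proportion abandoning for seizures) × (share of those who reach the maximum dose first). Assume 20% abandon in each arm, so the drugs are identical.

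- 80% reach the maximum first: 0.20 × 0.80 = 16%.
- 65%: 0.20 × 0.65 = 13%.
- 50%: 0.20 × 0.50 = 10%.

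The spurious difference is 3 points for 80% against 65%, and 6 points for 80% against 50% (6/16 = 38% relative). Counting at any dose returns 20% against 20% in every case.

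*Apparent hazard ratio.* Let f be the share of seizure-driven stops made below the maximum dose and so not counted, constant over time. With a true hazard ratio of 1, the apparent cause-specific ratio is (1 − fA)/(1 − fB).

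- 10% against 30%: 0.90/0.70 = 1.29.
- 20% against 40%: 0.80/0.60 = 1.33.
- 10% against 50%: 0.90/0.50 = 1.80.
- Equal shares: 1.00. Events are lost but there is no bias.

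*Chance of a false significant result.* Take two arms of 489 (Trial 1, section 9.2) and a true seizure-failure risk q, assumed between 10% and 25%. Counted events = 489 × q × [(1 − fA) + (1 − fB)]. Power is from the Schoenfeld formula at two-sided 5%.

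| fA vs fB | Apparent HR | Events, q = 10% to 25% | Chance of p < 0.05 with no true difference |
|---|---|---|---|
| 10% vs 30% | 1.29 | 78 to 196 | 20% to 42% |
| 20% vs 40% | 1.33 | 68 to 171 | 22% to 47% |
| 10% vs 50% | 1.80 | 68 to 171 | 68% to 97% |

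**The case against.** The strongest reply is that an endpoint may be narrower than permitted practice. Sections 2.4.1 and 7.7 grant clinical freedom, while 4.2 is a counting rule. A dose-qualified rule has a rationale, because giving up an under-titrated drug does not show that it failed. This stands as a reason to keep the dose-qualified version. It does not answer the gap: the permitted early switch has no stated classification.

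The maximum tolerated dose limb also counts patients whose titration was limited by side effects, so some stops below the recommended maximum do count. That reduces the loss without removing it.

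The illustration fixes abandonment at 20% in both arms. If clinicians really gave up sooner on one drug, its abandonment would probably rise too, and any-dose counting would then run against that drug. This also stands: any-dose counting is not free of unblinded behaviour, and neither version is sufficient alone.

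Three stronger readings are not supported.

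- A reader might infer that the maximum dose varies by site. Section 7.3 lists no maximum, but it says that doses outside a recommended range are highlighted in EpiNet, and section 7.2 points to national data sheets. Any variation shown is at most by country, and randomisation is stratified by country (6.3).
- A reader might infer that withdrawals for other reasons have no place in the analysis. Section 9.5 speaks of two main reasons and plans cumulative incidence, so a further cause is not excluded, and the detail can properly be left to the SAP.
- A reader might infer that bias between arms is established. It requires below-maximum switching to differ by drug. National habits alone are largely balanced by stratification, and the protocol gives no data on drug-specific habits.

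**Conclusion.** The point holds for secondary endpoints 4.2(a) and 4.2(b) and their analyses in section 9.5, in all five trials. As written, a permitted withdrawal or add-on for seizures below the maximum recommended or tolerated dose counts as failure under neither limb, which undercounts efficacy failure and sits badly with the pragmatic aim and with endpoint (g).

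The extent of undercounting is unknown. Under the assumed shares, the distortion between identical drugs ranges from none (equal shares) to 6 percentage points or an apparent hazard ratio of 1.80. These figures show sensitivity and are not estimates of what will happen.

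The primary endpoint, its intention-to-treat analysis and the sample sizes do not depend on this definition. It is a worthwhile, inexpensive correction to secondary endpoints and does not threaten the main conclusions.

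**What to change.** Reconcile section 4.2 with sections 2.4.1, 5.3.1 and 7.7, for endpoint counting only:

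1. For (a) and (b), pre-specify an analysis in which the seizure-control event is the first withdrawal of the allocated drug, or addition of a second AED, whose recorded reason is inadequate seizure control, whatever the dose. The adverse-event limb of (a) stays as it is.
2. Report this beside the dose-qualified version for each trial.
3. In the dose-qualified cumulative-incidence analysis, treat below-maximum efficacy switches and add-ons as a competing event, not as non-informative censoring. This will not equalise the recorded failure curves, but it shows how many patients leave by that route in each arm.

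The cost is endpoint and analysis wording. No new data item is needed for the any-dose version, because section 7.7 already requires the reason for each change. The downside is that the any-dose version counts some switches made before an adequate dose and still reflects unblinded decisions, which is why both versions should be shown. No dosing, switching or stopping rule changes.

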# **Focal onset seizure participants**

Lamotrigine (LTG), or Carbamazepine (CBZ), or Levetiracetam (LEV)

Generalised onset seizure participants, if valproate deemed an acceptable AED

Levetiracetam (LEV), or Valproate (SVA)

Generalised onset seizure participants, if valproate is NOT deemed an acceptable AED

Levetiracetam (LEV), or Lamotrigine (LTG)

Unclassified seizure participants, if valproate deemed an acceptable AED

Levetiracetam (LEV), or Lamotrigine (LTG), or Valproate (SVA)

Unclassified seizure participants, if valproate is NOT deemed an acceptable AED

Levetiracetam (LEV), or Lamotrigine (LTG)

**Primary Objective:** Time to 12 month remission - measured using data recorded in participant seizure diaries and seizure data collected at all follow up visits **Secondary Objectives:** 

- ? Time to treatment failure\*
- Time to treatment failure due to inadequate seizure control\*
- Time to treatment failure due to unacceptable adverse events\*
- Time to first seizure\*
- Time to 24 month remission\*
- Serious Adverse events (attributed to the trial medication or other anti-epileptic medication)\*
- Proportion of patients who achieve a 12 month remission by 18 months who have not changed to a different AED
- Quality Of Life (QOL)

\* Measured using information provided by the patient and clinicians

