# 7.4 Unblinding

EpiNet-First trials are open-label trials and therefore unblinding is not required.

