#### 10. PHARMACOVIGILANCE

All Serious Adverse Events (SAE) and Reactions (SARs) or Suspected Unexpected Serious Adverse Reaction (SUSARs) will be recorded and reported as secondary endpoints of the studies. Systematic collection of all adverse events or adverse reactions will not be performed, as the trial medications are in use worldwide and side effects are well established.

All adverse events deemed important by the local investigator should be recorded in the EpiNet record. Other adverse events reported to a physician can also be recorded in EpiNet as 'Drug Side Effects' in the Treatment form at the physician's discretion. This data, however, will not be collated and reported as an end-point of the EpiNet-First study. Quality of Life will be used as an assessment of a patient's overall tolerance to a drug versus seizure control.

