# **10.4 Reporting Procedures**

All SAEs which occur from the time of consent until the final follow-up visit will be reported. Depending on the nature of the event the reporting procedures below should be followed. Any questions concerning adverse event reporting should be directed to the coordinating centre in the first instance. A flowchart is given below to aid in determining reporting requirements.

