# 10.6 Responsibilities - Investigator

The Investigator is responsible for reporting SARs that are observed or reported during the study.

All SARs must be reported immediately by the investigator by completing the SAE/SAR page within EpiNet. The coordinating centre will be automatically notified via an alert sent via EpiNet.

All pregnancies, deaths or SAEs should be reported as described in sections

```
10.4.4, 10.4.5 and 10.4.6.
```

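### The SAE secondary endpoint has two incompatible definitions, and the narrower one depends on causality judged by unblinded investigators

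*Protocol*

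**What the plan says.** **Attributed events only.** Section 4.2(f) of the protocol gives the endpoint as "Serious Adverse events attributed to the trial medication or other anti-epileptic medication". The secondary objectives in the protocol summary (section 1) carry the same restriction.

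**All events.** The opening of section 10 says: "All Serious Adverse Events (SAE) and Reactions (SARs) or Suspected Unexpected Serious Adverse Reaction (SUSARs) will be recorded and reported as secondary endpoints". Section 10.4 sets the scope of collection: "All SAEs which occur from the time of consent until the final follow-up visit will be reported". Section 10.2 also makes all SAEs reportable.

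**Causality.** Section 10.2 gives the judgement to the investigator who cares for the participant, using the five grades of Table 2. No blinded or central adjudication is described. Section 7.4 states: "EpiNet-First trials are open-label trials and therefore unblinding is not required".

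**Analysis.** Section 9.5 sets out between-arm methods for the time-to-event outcomes, the 18-month proportion and quality of life. On SAEs it says: "Line listings will be prepared for all serious adverse events".

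**The concern.** A reader who follows section 4.2(f) and one who follows section 10 would report different numbers under the same endpoint name. If the choice is left until the data are in, it can be made knowing which version looks better.

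The attributed-only version also has a bias of its own. The person who decides whether an event counts knows which drug was given. The protocol itself describes distinct reputations for the drugs: severe skin reactions with carbamazepine and, to a lesser extent, lamotrigine, and harm to the unborn child with valproate. An investigator who expects harm from a drug may attribute more events to it. One who trusts a drug may attribute fewer. The arms can then differ, or appear alike, for reasons unrelated to the true rate of serious events.

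This matters more because section 10 does not collate non-serious adverse events as an endpoint. The other event-based tolerability endpoint, treatment failure due to unacceptable adverse events, is also defined in section 4.2(a) by attribution to the drug.

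**Working it through.** The protocol states no SAE rate and no attribution rate, so there is no planned figure to reproduce. The main check is to set the texts side by side.

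**1. Definitions**

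| Place in protocol | Which SAEs |
|---|---|
| Section 1, secondary objectives | attributed to trial drug or another AED |
| Section 4.2(f) | attributed to trial drug or another AED |
| Section 9.5, listings | all |
| Section 10, opening | all SAEs, SARs and SUSARs, as secondary endpoints |
| Sections 10.2 and 10.4 | all are reportable, from consent to final visit |

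Collecting all events while analysing a subset would be coherent. The contradiction is that section 10 calls the full set secondary endpoints, while sections 1 and 4.2(f) give that status to the subset.

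**2. What counts as attributed**

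Table 2 has five grades: unrelated, unlikely, possibly, probably, almost certainly. Section 10.3 sets a cut-off (possibly or above), but for SUSARs only. Section 4.2(f) names none, so even the narrow version is not fully defined.

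**3. Illustration of the bias (assumed rates)**

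Let r be the all-cause risk of an SAE, equal in both arms, with one SAE per affected patient. Let q1 and q2 be the probabilities that an SAE is attributed in each arm. The endpoint then shows risks r × q1 and r × q2, and

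risk ratio = (r × q2) / (r × q1) = q2 / q1.

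The true risk r cancels, so the spurious ratio is simply the ratio of attribution probabilities. The chance that it reaches two-sided 5% significance comes from the usual normal approximation for two proportions with n per arm:

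P = Φ((|p1 − p2| − 1.96 × SE0) / SE1), with p1 = r q1, p2 = r q2, SE0 = √(2 p̄(1 − p̄)/n), SE1 = √((p1(1 − p1) + p2(1 − p2))/n), where p̄ is the mean of p1 and p2.

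Arm sizes are the smallest and largest in section 9.2: 253 (Trial 2) and 489 (Trial 1).

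| r | q1 v q2 | Endpoint shows | Ratio | P, n = 253 | P, n = 489 |
|---|---|---|---|---|---|
| 10% | 10% v 20% | 1% v 2% | 2.0 | 15% | 25% |
| 10% | 20% v 30% | 2% v 3% | 1.5 | 11% | 17% |
| 5% | 30% v 40% | 1.5% v 2% | 1.33 | 6% | 9% |
| 20% | 30% v 50% | 6% v 10% | 1.67 | 38% | 64% |

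Under the same assumptions an all-cause comparison has ratio 1.0 and a nominal false-positive rate of 5%.

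**The case against.** **No data are lost.** All SAEs are recorded with their causality, deaths are reported, and the listings cover all SAEs. Either version could be produced later. This stands, and it is why the fix is cheap. It does not say which version is the endpoint.

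**Counting drug-attributed SAEs is a defensible pragmatic choice for well-known drugs, and all-cause counts are not free of judgement.** Section 10.1 counts precautionary admissions and other important medical events, and section 10.4.1 leaves out the treated disease unless it is worse than expected. This stands in part: all-cause SAEs depend less on unblinded judgement but are not independent of it, and they include unrelated events.

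**The illustration rests on invented rates, and small counts would seldom mislead.** The first half stands. On the second, 1% against 2% in Trial 1 means about 5 against 10 patients (489 × 0.01 = 4.9; 489 × 0.02 = 9.8), with z about 1.3 and p about 0.2. A single result like that proves little, but a doubled point estimate would still be reported.

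Three stronger readings are tempting, and the protocol does not support them.

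- A reader might infer from section 9.5 that SAEs will only be listed and never compared. The text plans listings but excludes no by-arm table, and it defers to a SAP that is not available here.
- A reader might infer that SAEs are the only event-based safety comparison. Treatment failure due to unacceptable adverse events is also compared by arm.
- A reader might take section 10.6, "The Investigator is responsible for reporting SARs that are observed or reported during the study", as a third definition of the endpoint. That section concerns reporting duties, and it goes on to require that deaths and SAEs be reported too.

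**Conclusion.** The concern holds in a limited form. Sections 1 and 4.2(f) contradict the opening of section 10 on what the SAE endpoint is; this follows from the text alone and needs no assumption. The attributed-only version is also open to bias, because causality is judged by investigators who know the treatment and no causality threshold is stated.

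The size of that bias cannot be known from the protocol. With assumed attribution differences of 10 to 20 percentage points, the spurious risk ratio runs from 1.33 to 2.0. That range assumes equal true risk and one SAE per affected patient; the direction could go either way. The problem lies in the definition of a secondary endpoint, not in data capture. Nothing here touches the primary endpoint or the sample size. The change should be made, but it is not critical to the trials.

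**What to change.** Use one definition in sections 1, 4.2(f) and 10: all SAEs regardless of attribution. State that they are summarised by randomised arm as the number and proportion of patients with at least one SAE, with a risk difference or ratio and its 95% confidence interval.

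Keep AED-attributed SAEs as a supplementary table, and state which grades of Table 2 count as attributed. Keep the line listings.

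The cost is a change of wording and one table per trial, with no new data. The downside is small: all-cause counts include unrelated events and are somewhat noisier.
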